3.3.4 CCI

3.3.4.1 Inflammatory and target engagement biomarkers

CCI

[figure not shown]
CCI

[figure not shown]
3.3.4.2 CCI

3.3.4.3 CCI

3.3.4.4 CCI

3.3.5 Safety endpoints

3.3.5.1 Adverse events

An adverse event is the development of any untoward medical occurrence in a subject or clinical study subject administered a medicinal product and which does not necessarily have a causal relationship with this treatment. An AE can therefore be any unfavourable and unintended sign

(e.g., an abnormal laboratory finding), symptom (e.g., nausea, chest pain), or disease temporally associated with the use of a medicinal product, whether or not considered related to the medicinal product. The term AE is used to include both serious and non-serious AEs and can include a deterioration of a pre-existing medical occurrence. An AE may occur at any time, including run-in or washout periods, even if no study treatment has been administered.

Serious adverse events (SAEs) will be collected from time of signature of informed consent (either the brief, pre-screening ICF or the full, screening ICF), throughout the treatment period and including the follow-up period. All non-serious AEs will be recorded from time of first dose of study treatment, throughout the treatment period and including the follow-up period. Adverse events (AEs) will be coded with the most up to date MedDRA version. For any additional details on AE reporting please refer to the study protocol.

The AEs are assigned to the analysis phases described in section [3.1.3](#), based on the AE start date as follows:

- If the AE start date is before the first dose of treatment date, then the AE is assigned to the pre-treatment phase,
- If the AE start date is on or after the first dose of treatment date through 28 days after last dose of treatment (inclusive), then the AE is assigned to the on-treatment phase,
- If the AE start date is more than 28 days after last dose of treatment, then the AE is assigned to the follow-up phase.

If the start date of an AE is completely missing, the AE is assigned as follows:

- If the AE end date is known and is before the first dose of treatment date, then the AE is assigned to the pre-treatment phase,
- If the AE end date is completely missing or if the AE end date is on or after the first dose of treatment date no assignation can be done.

The study day of start of the AE is calculated as the start date of the AE - date of the first dose of treatment +1 for AE started on or after day 1 and as the start date of the AE - date of the first dose of treatment for AE started before day 1. Study day of start of AE is calculated for complete dates only. Imputed dates should not be used. If one of the dates is missing or partially missing, the study day of start of the AE is missing.

All the AEs in the on-treatment and follow-up phases are considered treatment emergent adverse events (TEAEs).

The duration of AE is calculated as the end date of the AE – start date of the AE +1. Duration is calculated for complete dates only. Imputed dates should not be used. If one of the dates is missing or partially missing, the duration is missing.

The analysis will be based on as-treated population.

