3.1.1.2 Imputation of adverse event / concomitant medication start date

Missing start dates (where in eCRF UN, UNK and 0000 indicate unknown or missing Day, Month and Year respectively for partial missing dates, while completely missing dates would be left empty):

- Completely missing dates will not be imputed.
- If the day is missing and the month and year are different from the month and year of the first dose of study treatment, assume 01-MMM-YYYY. If the month and year are the same as the first dose of IP month and year and the end date (after any imputation) is on or after (including still on-going/ missing at the end of the study) the first dose of IP, then assume the date of the first dose of IP. If the month and year are the same as the first dose of IP month and year and the end date (after any imputation) is prior to the first dose of IP, then assume the end date for the start date.
- If the month is missing and the year is different from the year of first dose of IP, assume 01-JAN-YYYY of the collected year. If the year is the same as the first dose of IP and the end date (after any imputation) is on or after (including still on-going/ missing at the end of the study) the first dose of IP, then assume the date of the first dose of IP. If the year is

the same as the first dose of IP and the end date (after any imputation) is prior to the first dose of IP, then assume the end date for the start date.

After applying these rules, if the imputed AE start date is after a complete AE end date (or date of death or date of end of study), the imputed start date will be the same as the complete AE end date (or date of death or date of end of study); if the end date is missing and the imputed AE start date is after the end of study date then assume the same date as the study end date.

CCI

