3.5 Concomitant medications

The most up to date version of WHO Drug Dictionary (WHO-DD) is used to classify medications by World Health Organization (WHO) Anatomical Therapeutic Chemical (ATC) classification of ingredients.

The imputation method described in section [3.1.1.2](#) and [3.1.1.3](#) is used in case of medication start date or stop date partially missing. Completely missing concomitant medication start dates and stop dates are not imputed.

After the end date imputation, the medications will be classified as either prior or concomitant (but not both) according to its stop date. Concomitant medication is defined as any medication with a stop date on or after the first dose of study drug, or any medication taken prior to study

drug and that is ongoing. Medications with completely missing stop date are classified as concomitant.

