4.2.10.7 Adverse events

After having assigned the AEs to the corresponding analysis phase as described in section [3.3.5.1](#), the AEs will be summarized for each treatment group and overall (total will not include placebo subjects). The AEs tables will be based on the as-treated population except the AE by ADA tables which will be based on the Immunogenicity population. Summary tables will include AEs in the on-treatment phase and AEs in the follow-up phase.

Summary tables are listed below.

An overview table containing:

- Number and percentage of subjects with any AEs
- Number and percentage of subjects with any AEs with outcome of death
- Number and percentage of subjects with any SAE (including events with outcome = death)
- Number and percentage of subjects with any AEs leading to discontinuation of treatment
- Number and percentage of subjects with any AEs leading to withdrawal from study

Subjects with multiple events in the same category are counted only once in that category.
Subjects with events in more than 1 category are counted once in each of those categories.

An overview table containing:

- Any AE
- Any AEs with outcome of death
- Any SAE (including events with outcome of death)
- Any AE leading to discontinuation of treatment
- Any AE leading to withdrawal from study

Multiple events in the same category are counted multiple times in that category. Multiple events belonging to more than 1 category are counted multiple times in each of those categories.

The following summary tables will be presented by SOC and PT:

- The number and percentage of subjects with any AEs
- The number of AEs
- The number and percentage of subjects with AEs with outcome of death
- The number of SAEs
- The number and percentage of subjects with SAEs
- The number and percentage of subjects with SAEs, assessed by investigator as possibly related to investigational product
- The number and percentage of subjects with AEs leading to discontinuation
- The number and percentage of subjects with any bleedings (all events from bleeding event form or from adverse event form with SMQ= “Haemorrhages narrow”)
- The number and percentage of subjects with any injection site reactions (all events from ISR form or from adverse event form with HLT= “Injection site reactions”)
- Overall summary of number and percentage of subjects with any AEs by ADA (anti-drug antibody category)
- The number and percentage of subjects by ADA (anti-drug antibody category)

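### An AE with a completely missing start date gets no analysis phase unless it is known to have ended before first dose, so any such event would be left out of the AE summary tables

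*SAP*

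**What the plan says.** SAP 3.1.1.2 leaves a wholly absent AE start date alone: "Completely missing dates will not be imputed". SAP 3.3.5.1 then has a branch for exactly these records: "If the start date of an AE is completely missing, the AE is assigned as follows". The first bullet reads "If the AE end date is known and is before the first dose of treatment date, then the AE is assigned to the pre-treatment phase". The second bullet covers everything else, namely an end date that is also missing, or the case where "if the AE end date is on or after the first dose of treatment date no assignation can be done".

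The same section defines treatment-emergent AEs as those in the on-treatment and follow-up phases. SAP 4.2.10.7 limits the tables in the same way: "Summary tables will include AEs in the on-treatment phase and AEs in the follow-up phase". It separately provides a listing of every AE whatever its phase, and says that the AE analyses go into IDMC reports as well as the final analysis.

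On when collection starts, SAP 3.3.5.1 says "All non-serious AEs will be recorded from time of first dose of study treatment". Protocol 8.3.1 starts non-serious AE collection at randomization. SAEs are collected from the first consent form in both documents.

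**The concern.** A safety convention should resolve doubt about onset towards counting the event. This one resolves it towards leaving the event out, and it can only lower counts. It applies to every AE summary governed by the phase restriction: overall incidence, SAEs, AEs leading to discontinuation, and the bleeding and injection-site tables, which refer to all events from their forms but sit under the same restriction.

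The statement that no phase can be assigned is also stronger than the trial's design warrants. Non-serious AEs are not collected before Day 1, so the collection period itself tells us roughly when such an event began. A reaction at a study injection site cannot predate the first injection, yet without a start date it too gets no phase.

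Because the same tables go to the IDMC while the study is running, before final data cleaning, an unresolved start date is more plausible there than at database lock.

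**Working it through.** The plan states no figure to reproduce. The check follows the rules and then sets the partial-date and missing-date conventions side by side.

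**Rule chain**

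1. Start date wholly missing: not imputed (SAP 3.1.1.2).
2. Phase: pre-treatment if the end date is known and before first dose; otherwise none (SAP 3.3.5.1).
3. No phase means not a treatment-emergent AE (SAP 3.3.5.1) and not in the AE summary tables (SAP 4.2.10.7).
4. The all-AE listing still shows the event (SAP 4.2.10.7). The key-subject-information tables do not repeat the phase restriction, so their treatment of such an event is unclear. No section returns it to the other tables.

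**Partial against wholly missing start dates**

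| Start date | End date | Result |
|---|---|---|
| Month and year known, same as first dose | On or after first dose, or ongoing | Start set to first dose (3.1.1.2), on-treatment (3.1.3), in tables |
| Year only known, same as first dose | On or after first dose, or ongoing | Same |
| Nothing known | On or after first dose, or missing | No phase (3.3.5.1), not in tables |
| Nothing known | Before first dose | Pre-treatment (3.3.5.1), not in tables |

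In rows one and two onset could still have been before dosing, and the SAP settles that doubt by counting the event. In row three it settles the same kind of doubt by leaving the event out. An end date on or after first dose leads to inclusion under one rule and exclusion under the other.

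**How likely is true treatment emergence?**

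- Non-serious AEs: collected from first dose (SAP) or from randomization (Protocol 8.3.1). Randomization and first dose are both on Day 1 (Protocol 4.1 and 6.3.1), so the difference between the documents hardly matters here. An undated non-serious AE is almost certainly treatment-emergent.
- SAEs: collected from first consent, which may be at pre-screening, as early as Day -84 (Protocol Table 3). An undated SAE that ended after first dose may have begun before it.

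**Size**

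Let m be the share of true treatment-emergent AEs that have no start date and are not shown to have ended before first dose. The documents do not give m; the values below are assumptions.

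- Event counts: reported = (1 - m) x true. For m = 0%, 0.5%, 1% and 2%, the tables lose 0, 5, 10 and 20 of every 1,000 events.
- Subject counts: a subject drops out of a category only if all of his or her k events in it are undated. If each event has the same independent chance m of lacking a date, that probability is m^k, which is at most m. With m = 2%, k = 1 gives 2% and k = 2 gives 0.02 x 0.02 = 0.04%. The relative loss therefore lies between 0 and m. Without the independence assumption, the firm bound is that no more subjects are lost than there are undated events.
- Under the replacement rule below, the loss is 0 for every m.

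**The case against.** Several points on the other side stand.

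- **The records may not exist.** Start and stop dates are collected for every AE (Protocol 8.3.2), participants are asked about events since the previous visit (8.3.4), and source data verification is planned (Appendix A 7). Partial dates are imputed and do get a phase. A reader might infer that the AE counts are too low; the documents support only that they would be too low if such a record remains.
- **The events do not disappear from the report.** The all-AE listing shows them, so the loss is from the summary tables.
- **A reader might infer that every excluded event is a lost treatment-emergent event.** That fits non-serious AEs. It does not fit SAEs, which are collected from consent. Undated SAEs are also unlikely, because Protocol 8.3.2 collects several further dates for each SAE, and 8.3.7 requires immediate follow-up of missing information for fatal or life-threatening events.
- **A reader might set the rule against SAP 3.5, where "Medications with completely missing stop date are classified as concomitant", and call it the opposite convention.** It is not like for like. Medications are classified by stop date, and a missing stop date is consistent with continued use; AE phase depends on onset. The valid comparison is with the partial-date rule in 3.1.1.2.
- **No bias between arms is shown.** The rule is the same in every group, and the study is blinded to active versus placebo. The expected effect is slight under-ascertainment overall.

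These points limit the likely size. They do not supply a phase for the affected events, and they do not explain why partial and wholly missing dates are treated in opposite directions.

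**Conclusion.** The point holds as a conditional one. As written, SAP 3.3.5.1 would exclude from the treatment-emergent definition and the AE summary tables any AE with a wholly missing start date that is not known to have ended before first dose. This applies to IDMC reports and to the final analysis, and the direction is always downward.

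The size depends on a number that the documents do not give and that may be zero. Event counts fall by the affected share. Subject counts fall by between zero and that share, assuming that missing dates are independent across events. For non-serious AEs the excluded event is almost certainly treatment-emergent; for SAEs that cannot be assumed. The inconsistency with the SAP's partial-date rule is there on the page and does not depend on how many records are affected.

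**What to change.** Replace the second bullet under the missing-start-date rule in SAP 3.3.5.1 with: *If the start date is completely missing, the AE is assigned to the on-treatment phase unless its end date is before the first dose.*

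This brings the rule into line with 3.1.1.2, needs no new data and leaves dated AEs unchanged. Study day and duration stay missing for these events, because 3.3.5.1 derives them from complete dates only. If no such records exist, nothing changes.

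The cost is one sentence, plus the chance that a few events that began before dosing, mainly SAEs, are counted as treatment-emergent. For a safety table that is the more cautious error, and the listing lets a reader identify those events.

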3.3.5.2 Laboratory evaluations

Clinical laboratory safety tests are performed in a central and/or local clinical laboratory. A list of clinical laboratory safety tests is reported below:

Table 5 Clinical Laboratory Safety Test

Serum chemistry	Haematology	Coagulation Parameters (screening only)
S/P-Creatinine	B-Haemoglobin	International Normalized Ratio
S/P-Bilirubin, total	B-Leukocyte count	Activated Partial Thromboplastin Time
S/P- Alkaline Phosphatase (ALP)	B-Leukocyte differential count (absolute count)	
S/P- Aspartate Transaminase (AST)	B-Platelet count	
S/P- Alanine Transaminase (ALT)		
S/P-Albumin		
S/P-Potassium		
S/P-Calcium, total		
S/P-Sodium		
S/P- Creatine Kinase (CK)		
eGFR		
S/P, serum/plasma		

Additionally, fasting lipid panel will be included in serum chemistry:

- High density-lipoprotein (HDL)-Cholesterol Direct, 4th Generation
- Triglycerides
- Cholesterol
- Low density lipoprotein (LDL)-Cholesterol

Laboratory data are assigned as per timepoint related to analysis visits (Table 3).

The analysis will be based on as-treated population.

Occurrences of AST or ALT $\geq 3 \times$ Upper limit of normal (ULN) together with total bilirubin $\geq 2 \times$ ULN are reported as SAEs (Potential Hy's law) as described in the study protocol.

3.3.5.3 Vital signs

Vital signs include:

- Systolic blood pressure (mmHg)
- Diastolic blood pressure (mmHg)
- Heart rate (beats/min)
- Height (cm)
- Weight (kg)
- BMI (kg/m^2)

Vital signs parameters are assigned to the analysis visits as described in section 3.1.2. Change from baseline is defined as the post-baseline visit value minus the baseline value.

Additionally, vital signs values will be classified as normal (if value is within normal reference range), low (if value is below the normal reference range), and high (if value is above the normal reference range) according to the normal reference ranges ([Table](#)):

Table 6 **Vital signs normal reference ranges**

Parameter	Normal Reference Ranges
Systolic blood pressure	90 – 130 mmHg
Diastolic blood pressure	50 – 80mmHg
Heart rate	50 – 100 bpm
BMI	18 – 25 kg/m^2

The analysis will be based on as-treated population.

3.3.5.4 ECG

Overall ECG evaluation (normal, abnormal) is collected. If abnormal, also reason and clinically significance is collected.

ECG evaluations are assigned as per timepoint related to analysis visits (Table 3).

ECG last observation on treatment is defined as last available value among those in the on-treatment analysis phase.

The analysis will be based on as-treated population.

3.4 Exposure and treatment compliance

As per study protocol, subjects will receive study treatment directly from the investigator or designee, under medical supervision, at the clinic. They will receive the subcutaneous (SC) injections from Day 1.

Study treatment will be given at the following study visits:

- Day 1
- Day 29
- Day 57
- Day 85
- Day 113
- Day 141
- Day 169
- Day 197
- Day 225

3.4.1 Exposure

Exposure and extended exposure (days) is calculated only for subjects in the as-treated population.

Exposure is calculated as the study treatment last dose date minus study treatment first dose date plus one. If any of the first or last dates are missing or partially missing, then exposure to study treatment is set to missing.

Cumulative exposure is also computed based on exposure, using the following duration (days) categories:

- ≥ 29
- ≥ 57

- ≥ 85
- ≥ 113
- ≥ 141
- ≥ 169
- ≥ 197
- ≥ 225

Extended exposure is calculated as the study treatment last dose date minus study treatment first dose date plus 28. If any of the first or last dates are missing or partially missing, then extended exposure to study treatment is set to missing.

Cumulative extended exposure is also computed based on extended exposure, using the following duration (days) categories:

- ≥ 56
- ≥ 84
- ≥ 112
- ≥ 140
- ≥ 168
- ≥ 196
- ≥ 224
- ≥ 252

3.4.2 Compliance

Considering the way of the treatment administration, compliance to the treatment will not be analysed and not provided in listing.

3.5 Concomitant medications

The most up to date version of WHO Drug Dictionary (WHO-DD) is used to classify medications by World Health Organization (WHO) Anatomical Therapeutic Chemical (ATC) classification of ingredients.

The imputation method described in section [3.1.1.2](#) and [3.1.1.3](#) is used in case of medication start date or stop date partially missing. Completely missing concomitant medication start dates and stop dates are not imputed.

After the end date imputation, the medications will be classified as either prior or concomitant (but not both) according to its stop date. Concomitant medication is defined as any medication with a stop date on or after the first dose of study drug, or any medication taken prior to study

drug and that is ongoing. Medications with completely missing stop date are classified as concomitant.

4 ANALYSIS METHODS

4.1 General principles

Data will be summarized using descriptive statistics at each visit. For the analyses and listings, placebo will be the 3 injection/volume-matched placebo groups pooled. Treatment groups will be:

- MEDI6570 with dose **CCI** and placebo for ITT, CTA analysis, Echocardiogram analysis populations. In these analyses, subjects initially randomized to the **CCI** group who consented to CSP amendment 1 and were switched to **CCI** dose were analysed according to the **CCI** group. For the safety and efficacy analyses, the number of subjects randomized to the **CCI** group who consented to amendment 1 of the CSP and switched to the **CCI** dose is specified.
- MEDI6570 with dose **CCI** or **CCI** and placebo for as treated, Per-protocol CTA analysis and Immunogenicity populations. In these analyses patients treated within **CCI** group who received at least one **CCI** dose during the study will be analysed according to the **CCI** group.
- MEDI6570 with dose **CCI** or **CCI** and **CCI** (listing only) and placebo for PK and **CCI** analysis populations. Subjects who only received **CCI** will be analysed according to the **CCI** group. Subjects who received both **CCI** and **CCI** doses during the study will be analyses as a separate **CCI** group. Due to few subjects in **CCI** treatment group they will not be included in summary table and figures as well as in modelling outputs. They will be included in listings only.

For continuous variables and unless otherwise specified descriptive statistics will include the number of subjects (n), mean, SD, median, minimum, and maximum. The 1st and 3rd quartiles will be added to exposure and ADA only if not requested otherwise. If the parameter is assumed to be log-normally distributed, the descriptive statistics will additionally include geometric mean (GeoMean) and geometric coefficient of variation (GeoCV). For geometric mean calculation, variables records with zero value will be imputed by half of the minimum of the non-zero records prior to the log-transformation.

Decimal places will always apply the following rules:

- n will be presented as integer.

- Percentage (including CV and GeoCV) will be presented with 1DP except Kaplan Meier (KM) estimate that will be with 2DP.
- For derived variables, the precision of the calculated variable will be one more than the least number of decimal places among the raw data used for calculation with a maximum of 3DP.
- Ratio (including hazard ratio and crude rate) will be presented with 2DP.
- Min and max will be presented as the original value. All other statistics (mean, SD, median, Q1, Q3, GeoMean, LSmeans, LSGeomean, Standard error (SE), geometric LSmeans, CI bounds) will be presented as the original value +1 additional decimal place considering a maximum of 3 DP for raw/derived and 4 DP for the other statistics.
- P-value will be presented with 3DP. If p-value is lower than 0.001, will be displayed “<0.001” and if p-value is higher than 0.999 or equal to 1, will be displayed “>0.999”.
- If parameter unit is percentage (such as LVEF or GLS) the original value has 1DP.

Normality will be defined a priori and will be assessed graphically using “quantile–quantile” plots (Q-Q plots) & histogram and by Tests of Normality for primary efficacy endpoint (NCPV_{MD}). If NCPV_{MD} shows large departure from distribution assessment, the parameter will be log-transformed and thus reported in the modeling as a log-normally distributed parameter (e.g. LSGeomean, ...). If the assumption of normal distribution of NCPV_{MD} holds, summary statistics will report the values in original scale (e.g. GeoMean, GeoCV, ...). Finally, if primary efficacy endpoint (NCPV_{MD}) will not follow the normal distribution, subsequently the distribution of NCPV global and LAPV will be assumed as log-normally distributed because are subset of non-calcified plaque. .

All efficacy, exploratory and safety endpoints will be summarized by treatment group and at each visit as appropriate using descriptive statistics as above. Except otherwise specified, unscheduled visits will only be listed. For continuous variables, descriptive statistics will be provided for the observed values, the changes from baseline and the percent change from baseline (where appropriate).

The definition of the change from baseline will be related on the normal-/log-normal distribution of the evaluated variables, as following:

- for normally distributed variable: change from baseline, is defined as post-baseline visit value minus baseline value.

- for log-normally distributed variable: change from the baseline is defined as the logarithmic transformation of the value of the visit after the baseline value minus the logarithmic transformation of the baseline value.

For the observed variable (log-normally distributed) the descriptive statistics also include the GeoMean and the GeoCV% calculated as follows:

